0.8	05May2020	
1) Added details on the analysis for neurological examination results in Section 9.4 Physical Examination.2) Added presentation of FSHD specific history in Section 6.2.3) Updated Section 4.7 on sample size computation based on Version 3.0 of the protocol.4) Added details about inclusion of open-label extension phase but a separate SAP will be created for this.5) Updated SAP according to protocol Version 4.0 (COVID-19 Pandemic Emergency Amendment)
a. Extended randomized placebo-controlled period from 24 to 48 weeks in Section 3.1, 3.2, 4.4, 4.8, 7.2.1, 8, 9, and 11.b. Added Open-label Losmapimod (Pre-COVID-19) Analysis Set in Section 4.9.6 and 8.Muscle biopsy to support the primary endpoint is updated to be performed on Week 16 or 36 for those subjects unable to have the biopsy at Week 16 due to the COVID-19 pandemic.

		
c. Added interim analysis to be performed after a minimum of 22 paired muscle biopsies have been collected.d. Added hypothesis testing on primary and select secondary and exploratory endpoints in Section 8.1.e. Removed measurement of the metabolite GSK198602 in Section 2, 3.2 and 10.f. Updated Appendix 15.6 to include the latest schedule of events.g. Updated Appendices 15.7-15-9 to include the additional outputs and additional column to identify the outputs needed for topline and IA deliveries.
1.0	28May2020	Approved version

TABLE OF CONTENTS

LIST OF ABBREVIATIONS	VII
1. INTRODUCTION.....	1
2. OBJECTIVES	1
2.1. PRIMARY OBJECTIVES	1
2.2. SECONDARY OBJECTIVES	2
2.3. EXPLORATORY OBJECTIVES	2
3. INVESTIGATIONAL PLAN	2
3.1. OVERALL STUDY DESIGN AND PLAN.....	2
3.2. STUDY ENDPOINTS	4
3.2.1. Primary Endpoint	4
3.2.2. Secondary Endpoints	4
3.2.3. Exploratory Endpoints	5
3.3. TREATMENTS.....	6
4. GENERAL STATISTICAL CONSIDERATIONS	6
4.1. REPORTING CONVENTIONS	6
4.2. HANDLING OF MISSING DATA	7
4.3. BASELINE, STUDY DAY, AND CHANGE FROM BASELINE DEFINITIONS.....	7
4.4. VISIT WINDOWS	8
4.5. MULTIPLE VALUES	8
4.6. SUBGROUP	8
4.7. SAMPLE SIZE	9
4.8. RANDOMIZATION, STRATIFICATION, AND BLINDING	9
4.9. ANALYSIS SET	10
4.9.1. Full Analysis Set (FAS)	10
4.9.2. Per Protocol Set (PPS)	10
4.9.3. Safety Analysis Set	10
4.9.4. Pharmacokinetics Analysis Set	10
4.9.5. Pharmacodynamics Analysis Set	11
4.9.6. Open-label Losmapimod (Pre-COVID-19) Analysis Set	11
5. SUBJECT DISPOSITION	11

List of Abbreviations

AE	adverse event
AESI	adverse event of special interest
ANCOVA	Analysis of Covariance
ATC	Anatomical Therapeutic Chemical
BID	twice daily
BLQ	below the limit of quantitation
BMI	body mass index
CI	confidence interval
COA	clinical outcome assessment
COVID-19	coronavirus disease 2019
CRF	case report form
DUX4	double homeobox 4
ECG	electrocardiogram
FAS	full analysis set
FSHD	facioscapulohumeral muscular dystrophy
FSHD-HI	FSHD Health Index
IRT	Interactive Response Technology
LMV	lean muscle volume
LOCF	Last Observation Carried Forward
LS	least-squares
MedDRA	Medical Dictionary for Regulatory Activities
MFF	muscle fat fraction
MFI	muscle fat infiltration
MFM	Motor Function Measure
MRI	Magnetic Resonance Imaging
MMRM	Mixed Effect Model for Repeated Measures
MSK	musculoskeletal
OL	open-label
OLE	open-label extension
PGIC	Patient's Global Impression of Change
PO	orally
PPS	per protocol set
PT	preferred term
RWS	Reachable Workspace
RSA	relative surface area
SAE	serious adverse event
SAP	statistical analysis plan
SAS	Statistical Analysis Software
SD	standard deviation
SE	standard error
SOC	system organ class
SRC	Safety Review Committee
TEAE	treatment-emergent adverse events
TUG	Timed Up and Go
WHODD	World Health Organization drug dictionary

1. Introduction

This study is being conducted under the sponsorship of Fulcrum Therapeutics (Fulcrum) in accordance with applicable standard operating procedures. Statistical analyses are being conducted under contract with [REDACTED] Inc., in collaboration with Fulcrum.

The Clinical, Data Management, and Biostatistics departments at [REDACTED] will work diligently and collaboratively with Fulcrum to ensure that the data collected and analyzed for this study are of the highest quality possible. This will be accomplished in part by having thorough edit checks written, programmed, and updated as needed.

This Statistical Analysis Plan (SAP) is based on the protocol version 4.0 (COVID-19 Pandemic Emergency Amendment), dated 10Apr2020. This SAP is for the randomized, placebo-controlled treatment period. A separate SAP will be written for the open-label extension (OLE).

Facioscapulohumeral muscular dystrophy (FSHD) is a rare disabling disease with an estimated worldwide population prevalence of between 1:15,000 and 1:20,000 ([Statland and Tawil, 2014](#)), or approximately 16,000 to 21,000 affected individuals in the United States. FSHD is characterized by descending progressive skeletal muscle weakness affecting the face, shoulders, arms, and trunk, followed by weakness of the distal lower extremities and pelvic girdle. FSHD is caused by aberrant overexpression of the double homeobox 4 (DUX4) gene, a homeobox transcription factor. DUX4 is located within D4Z4 macrosatellite repeats on chromosome 4q35 and is not normally expressed in adult skeletal muscle when the number of repeats is >10. Approximately 95% of patients with FSHD have type 1 (FSHD1), in which the D4Z4 repeat array is contracted to 1 to 10 units on one allele ([Lemmers et al, 2010](#); [Statland and Tawil, 2014](#)). FSHD patients carrying a smaller number of repeats (1 to 3 units) are, on average, more severely affected ([Tawil et al, 1996](#)).

There are currently no approved disease-modifying treatments for FSHD. Fulcrum is developing losmapimod, a selective p38 α/β inhibitor, which is predicted to reduce DUX4 in affected skeletal muscle. It is anticipated that the proposed human dose of losmapimod for FSHD at 15 mg orally (PO) twice daily (BID) will provide drug concentrations in skeletal muscles sufficient to significantly inhibit p38 α/β and reduce aberrant expression of DUX4.

The term study drug that is being used throughout this document refers to losmapimod and/or placebo.

2. Objectives

2.1. Primary Objectives

The primary objective of the placebo-controlled treatment period is to evaluate the efficacy of losmapimod in inhibiting or reducing expression of DUX4, the root cause of FSHD, as measured by a subset of DUX4-regulated gene transcripts in skeletal muscle biopsies from FSHD1 subjects.

2.2. Secondary Objectives

The secondary objectives of the placebo-controlled treatment period are:

- To evaluate the safety and tolerability of losmapimod in FSHD1 subjects.
- To evaluate the change from baseline in muscle fat fraction (MFF), lean muscle volume (LMV) and muscle fat infiltration (MFI) in FSHD1 subjects, as measured by musculoskeletal (MSK) magnetic resonance imaging (MRI);
- To evaluate the plasma concentrations of losmapimod in FSHD1 subjects;
- To evaluate the levels of losmapimod in skeletal muscle in FSHD1 subjects; and
- To evaluate losmapimod target engagement in blood and in skeletal muscle in FSHD1 subjects.

2.3. Exploratory Objectives

The exploratory objectives of the placebo-controlled treatment period are:

- To evaluate the change from baseline in the following clinical outcome assessments (COAs):
 - Reachable Work Space (RWS) with and without weights
 - Classic and FSHD Timed Up and Go (TUG)
 - Muscle strength by hand-held quantitative dynamometry
 - Motor function Measure (MFM) Domain 1
 - FSHD Health Index (FSHD-HI)
 - Patients' Global Impression of Change (PGIC)
- To evaluate the change from baseline of inflammatory, immune, apoptotic, and muscle disease transcripts in muscle biopsy and circulating proteins in plasma and serum.

3. Investigational Plan

3.1. Overall Study Design and Plan

This study will be conducted in 2 parts: a randomized, double-blind placebo-controlled treatment period for 48 weeks, followed by a losmapimod open-label treatment period with a study population of males and females between 18 and 65 years of age at enrollment, inclusive, who have confirmed diagnosis of FSHD1 with 1 to 9 repeats via assessment of the size of the D4Z4 array on chromosome 4; a clinical severity score of 2 to 4 (RICCI score; range 0-5), inclusive, at screening; and a MRI eligible muscle for biopsy, as determined by a central reader.

During the placebo-controlled treatment period, approximately 76 subjects with FSHD1 will be randomized 1:1 to receive 15 mg PO of losmapimod (n=38) or placebo (n=38) tablets BID for 48 weeks. At the time of the latest protocol amendment (Version 4.0; 10Apr2020), enrollment was completed, a total of 80 subjects have been enrolled.

Once subjects reach Week 48, they will have the option to roll over into the open-label extension, with all subjects receiving 15 mg losmapimod PO BID. Subjects who wish to roll over into the

open-label extension must complete all procedures from the Week 48 end of placebo-controlled treatment period/start of open-label extension visit. Prior to the COVID-19 pandemic, subjects who reached the Week 24 visit had the option to roll over into the OLE. Subjects who have already rolled over to the OLE prior to the COVID-19 pandemic (n=12) will remain on open label treatment. Their next clinic visits will follow the assessments for the Week 36 and Week 48 visits in the placebo-controlled portion of the study in the COVID-19 Pandemic Emergency protocol version 4.0. These subjects will not undergo the Week 36 biopsy. Subjects who did not roll over prior to the COVID-19 pandemic, and thus are still on the randomized treatment, will continue on the randomized treatment and roll over into the OLE at the Week 48 visit. Please see the COVID-19 Pandemic Emergency protocol version 4.0 for further details.

[figure not shown]
The placebo-controlled treatment period will include a 4-week screening period and a 24 or 48-week placebo-controlled treatment period. Subjects who rolled over to the OLE portion of the study prior to the COVID-19 pandemic (under protocol version 3.0) have completed a 4-week screening period followed by a 24-week placebo-controlled treatment period.

Blood samples for pharmacokinetics (losmapimod concentrations) endpoints will be collected at Day 1, Week 4, Week 16, and Week 36 at the following timepoints: immediately pre-dose and 4 hours (± 30 minutes) after administration of the study drug. Blood samples for target engagement will be collected at Day 1 and Week 16 or Week 36 at the following timepoints: immediately pre-dose and 4 hours (± 30 minutes) after administration of the study drug. Musculoskeletal MRIs will be performed at screening, Week 12, Week 24, and Week 48. Muscle biopsies will be taken at Day 1 and Week 16, or at Day 1 and Week 36 if the muscle biopsy could not be performed at Week 16 due to the COVID-19 pandemic.

Safety and tolerability will be evaluated based on the assessment of adverse events (AEs), AEs of special interest (AESIs), serious adverse events (SAEs), laboratory tests, electrocardiogram (ECGs), vital signs, and physical examinations.

A schematic of the study design of the placebo-controlled treatment period is presented in [Figure 3-1](#).

Figure 3-1: Schematic of Study Design

Abbreviations: BID, twice daily; MRI, magnetic resonance imaging; OLE, open-label extension

During the open-label extension, subjects will be asked to attend clinic visits approximately every 12 weeks, and MRI will take place every 24 weeks. Study drug (open-label losmapimod) will be administered BID and should be taken with food. Subjects will remain in the open-label extension until study drug approval or until the study is discontinued by the Sponsor. All subjects who complete or discontinue from treatment will be asked to complete a 7-day safety follow-up period.

3.2. Study Endpoints

3.2.1. Primary Endpoint

The primary endpoint of the placebo-controlled treatment period is the change from baseline in DUX4 activity in affected skeletal muscle at Week 16 or Week 36, as measured by QRT-PCR in a panel of DUX4-regulated gene transcripts.

3.2.2. Secondary Endpoints

The secondary endpoints of the placebo-controlled treatment period are as follows:

- Safety and tolerability of losmapimod as defined by the following:
 - Type, frequency, severity, seriousness, and relationship of AEs to losmapimod;
 - Incidence of AESI;
 - Number of subjects who prematurely discontinue study drug due to an AE; and
 - Frequency of clinically significant changes in laboratory test, ECG, vital sign, and physical examination results

- Change from baseline in MFF, LMV, and MFI at Week 12, Week 24 (if applicable) and Week 48;
- Plasma concentrations of losmapimod at Week 4, Week 12, Week 16, Week 24, Week 36, and Week 48;
- Concentrations of losmapimod in skeletal muscle biopsy at steady state at Week 16 or Week 36;
- Target engagement parameters in blood, and skeletal muscle biopsy at Week 16 or Week 36.

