7.6.6 Safety Analyses

Safety data in the placebo-controlled treatment period will be analyzed using the safety analysis set and summarized by treatment group and visit (if applicable) using descriptive statistics. Safety data in the OLE will be analyzed using the open-label analysis set.

Treatment-emergent AEs will be summarized by MedDRA system organ class and preferred term; separate summaries will be produced for treatment-related AEs, AESIs, SAEs, and discontinuations due to AEs. Laboratory tests, vital signs, findings from physical examinations, and ECGs will be summarized for changes over time during treatment using descriptive statistics.

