8.5. Inflammatory, Immune, Apoptotic, and Muscle Disease Transcripts

The analysis of these exploratory endpoints will be described in a separate document.

9. Safety Analysis

All summaries of safety data will use the Safety Analysis Set and will be presented by treatment.

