9.2.1. Hematology

The following laboratory tests will be included: hemoglobin (including mean corpuscular volume), mean corpuscular hemoglobin, mean corpuscular hemoglobin concentration, hematocrit, red blood cell count, total white blood count, platelet count, differential blood counts, including basophils, eosinophils, neutrophils, lymphocytes, and monocytes.

Summary tables presenting observed values and changes from baseline will be presented for hematologic tests with numeric values by treatment group for subjects in the Safety Analysis Set. Changes from baseline to each scheduled post-baseline visit will be presented. All hematology data by subject will also be presented in a listing.

The clinical assessment of ‘Low’, ‘Normal’, or ‘High’ relative to the reference range will be summarized in shift tables comparing the baseline results to maximum value post-baseline for those subjects with results at both visits.

All hematology data by subject will be presented in a listing.

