9.2.2. Serum Chemistry

The following laboratory tests will be included: glucose, sodium, potassium, calcium, inorganic phosphate, total protein, albumin, blood urea nitrogen, creatinine, total bilirubin, alkaline phosphatase, aspartate aminotransferase, gamma-glutamyl transferase, and creatinine phosphokinase.

Summary tables presenting observed values and changes from baseline will be presented for serum chemistry tests with numeric values by treatment group for subjects in the Safety Analysis Set. Changes from baseline to each scheduled post-baseline visit will be presented. All chemistry data by subject will also be presented in a listing.

The clinical assessment of ‘Low’, ‘Normal’, or ‘High’ relative to the reference range will be summarized in shift tables comparing the baseline results to maximum value post-baseline for those subjects with results at both visits.

Results indicating liver-related abnormalities (i.e., ALT, AST, Total Bilirubin, and/or Alkaline Phosphatase) will also be summarized separately. A newly notable laboratory abnormality is defined as an abnormality observed post baseline that meets the notable criteria in [Table 9-1](#) and that did not exist at baseline. Subjects can still meet the criteria for a newly notable laboratory abnormality if the baseline value is missing. The table below displays the general variables and thresholds of interest. Subjects are considered to have notable laboratory abnormalities if his/her response falls within the specified definitions at least once during the treatment period.

Table 9-1: Notable Criteria for Laboratory Data Abnormalities – Liver Function Tests

Laboratory Variable	SI Units
AST	$\geq 3 \times \text{ULN}$
ALT	$\geq 3 \times \text{ULN}$
Total Bilirubin	$\geq 2 \times \text{ULN}$
Alkaline Phosphatase (ALP)	$\leq 2 \times \text{ULN}$
ALT or AST $> 3 \times \text{ULN}$ and total bilirubin $> 2 \times \text{ULN}$ and ALP $< 2 \times \text{ULN}$ (potential DILI or Hy's law case)	

All chemistry data by subject will be presented in a listing.

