9.3. Vital Sign Measurements

Summary tables will be presented for vital sign data, including pulse rate, respiration rate, blood pressure, and temperature by treatment for subjects in the Safety Analysis Set. Observed results at each visit will be presented. Change from baseline to each post-dose assessment will also be presented. All vital sign data by subject will also be presented in a listing.

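### Apart from the liver thresholds and ECG categories, the SAP plans no dedicated by-arm count of clinically significant safety changes, although that frequency is a named part of the secondary safety endpoint

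*SAP*

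**What the plan says.** Protocol 7.1.2 and SAP 3.2.2 define safety and tolerability through four components. Three concern adverse events (their type and frequency, those of special interest, and discontinuations due to them). The fourth is "Frequency of clinically significant changes in laboratory test, ECG, vital sign, and physical examination results".

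Protocol 7.6.6 states the analysis more loosely: laboratory tests, vital signs, physical findings and ECGs "will be summarized for changes over time during treatment using descriptive statistics". SAP section 9 opens with the rule that "All summaries of safety data will use the Safety Analysis Set and will be presented by treatment". The methods by domain are:

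- Hematology (SAP 9.2.1): "Summary tables presenting observed values and changes from baseline will be presented for hematologic tests with numeric values by treatment group". Low, Normal or High status "will be summarized in shift tables comparing the baseline results to maximum value post-baseline for those subjects with results at both visits". Coagulation (9.2.4) refers back to this method.
- Chemistry (SAP 9.2.2): the same, and in addition "Results indicating liver-related abnormalities (i.e., ALT, AST, Total Bilirubin, and/or Alkaline Phosphatase) will also be summarized separately", using the per-subject criteria of Table 9-1.
- Urinalysis (SAP 9.2.3): observed values and changes from baseline.
- Vital signs (SAP 9.3): "Observed results at each visit will be presented. Change from baseline to each post-dose assessment will also be presented".
- Physical examination (SAP 9.4): each body system as normal, abnormal or not done, plus numeric muscle scores from the neurological examination.
- ECG (SAP 9.5): descriptive summaries, number and percentage in each overall-evaluation category (one of which is abnormal and clinically significant), and QTcF bands.

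**The concern.** A frequency needs a rule for what counts and a table that counts it. The SAP supplies both for liver tests and ECG and neither for the other domains named in the same endpoint. A reader of the study report could see average changes, extremes and, for some tests, reference-range shifts, but could not read off how many subjects per arm had a clinically significant change in a given laboratory test, vital sign or body system. At stake is whether a named secondary safety component can be reported as it is defined.

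**Working it through.** No formula applies, and the plan states no figure to reproduce. The check sets each domain of the endpoint against SAP 9.2 to 9.5 and the planned tables in SAP 15.8.

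| Group | Planned tables (SAP 15.8) | Planned content (SAP 9) | Direct count of significant or notable change |
|---|---|---|---|
| Liver chemistry | 14.3.4.2.1 to 14.3.4.2.3 | values, changes, shifts, Table 9-1 thresholds | yes |
| ECG | 14.3.5.3.1 to 14.3.5.3.3 | values, changes, evaluation categories, QTcF bands | yes |
| Hematology | 14.3.4.1.1, 14.3.4.1.2 | values, changes, shifts | no |
| Coagulation | 14.3.4.3 | as hematology, by reference | no |
| Other chemistry | 14.3.4.2.1, 14.3.4.2.2 | values, changes, shifts | no |
| Urinalysis | 14.3.4.4 | values, changes | no |
| Vital signs | 14.3.5.1 | values, changes | no |
| Physical examination | 14.3.5.2.1, 14.3.5.2.2 | normal/abnormal/not done; muscle scores | no |

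Two of eight groups have a direct count; 8 − 2 = 6 do not. The visible text of the SAP addendum adds no safety analysis.

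Next, what the other planned outputs can show for those six groups.

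1. **Adverse event tables.** Protocol 6.2.2 has laboratory and other safety results, vital signs included, recorded as adverse events when the investigator judges them clinically significant; Protocol 6.2.1.4 adds physical examination findings. They then enter the by-arm tables of SAP 9.1.1. Those tables are organised by system organ class and preferred term, so they do not separate a laboratory or vital sign finding by assessment. Protocol 6.2.2 also exempts significant findings associated with the underlying disease unless they are more severe than expected. Creatine phosphokinase is in the chemistry panel of this muscle-disease trial, so the exemption may matter there; the documents do not say how often it would apply.

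2. **Shift tables.** These compare baseline with the maximum post-baseline value. A subject who starts Normal appears as a shift to Low only if every post-baseline value is Low. Protocol Table 13-1 schedules hematology at Weeks 4, 12, 16, 24, 36 and 48, which is six post-baseline visits. Five Low results and one Normal result would be tabulated as Normal to Normal. A fall in hemoglobin, neutrophils or platelets can therefore be missed.

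3. **Minimum and maximum.** SAP 4.1 includes both in every continuous summary, so one extreme low and one extreme high per arm and visit will be visible. They do not say how many subjects were affected. Under SAP 4.5, by-visit safety summaries keep the first non-missing value in a window, so a later unscheduled abnormal value in the same window drops out of that table.

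4. **Listings.** SAP 4.1 puts repeat and unscheduled assessments in the listings, so nothing is lost at subject level, but a listing is not a count by arm.

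**The case against.** The strongest reply is that the component is already reported. Under Protocol 6.2.2, clinically significant is an investigator's judgment and such findings become adverse events, which SAP 9.1.1 tabulates by arm with numbers and percentages. The SAP also follows Protocol 7.6.6, which asks only for descriptive statistics. The endpoint is descriptive and outside the testing hierarchy of SAP 8.1, and the table shells, kept in a separate document, may hold more detail.

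Much of this stands, and it rules out three stronger readings that a reader might infer:

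- That the SAP offers only means and reference-range shifts. It does not: Table 9-1 sets per-subject liver thresholds, and SAP 9.5 counts ECG categories.
- That significant changes are not tabulated by arm at all. Those recorded as adverse events are.
- That a few large individual changes would be lost in an arm mean. The summaries show minimum and maximum, so an isolated extreme value retained for a visit is visible. Nor does serum creatinine make the case: Protocol 1.5 describes a small rise of 1% to 7%, and mean change with a baseline-to-maximum shift suits an upward drift.

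The reply also limits the remedy: numeric limits alone would measure something other than the investigator's judgment.

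It does not close the gap. SAP 3.2.2 lists this frequency apart from the adverse event components and nowhere names the adverse event tables as its source. Those tables neither isolate the findings by assessment nor include those exempted as disease-related.

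**Conclusion.** The point holds in a limited form. In six of the eight assessment groups the SAP plans no dedicated by-arm count of clinically significant changes, although their frequency is a named part of the secondary safety endpoint. They surface only indirectly, and the maximum-only shift tables are weak for falls. This is a minor, descriptive safety-reporting correction with no bearing on the primary analysis, the type I error or the key endpoints. It carries no numerical effect size, because the documents give no expected rate of such changes.

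The conclusion assumes that the table shells and eCRF, which are not among the documents, contain no count beyond the titles in SAP 15.8. It also reads the safety rule in SAP 4.5 as keeping the first value within each window.

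**What to change.** In SAP 9.2 to 9.4 and 15.8, add by-arm n (%) tables of subjects with at least one clinically significant on-treatment change, per laboratory parameter, vital sign and body system. Use all scheduled and unscheduled values, and count both directions.

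- Base the count on the investigator's clinical-significance judgment under Protocol 6.2.2, identified by assessment type. If the eCRF carries no such flag, map adverse event records to assessment type in a blinded review before database lock, and state that disease-attributed findings are then not captured.
- Where values are numeric, add pre-set notable limits as a supplement, as Table 9-1 does for liver tests, and fix them before unblinding.
- In the shift tables, add the minimum post-baseline value beside the maximum.

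The least that would serve is a sentence in SAP 9 saying that the component is reported through treatment-emergent adverse events and how those are identified; that would leave the exempted findings and the shifts to Low unaddressed.

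The cost is SAP wording, a few extra tables and agreement on limits. The assessments are already collected. Physical examination counts will be sparse, because Protocol Table 13-1 schedules the full examination only at screening and at a safety follow-up that subjects entering the extension do not attend.
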